Precipitation of Opioid Withdrawal: Opioid-dependent and opioid-using patients, including those being treated for alcohol dependence, should be opioid-free before starting Vivitrol® treatment, and should notify healthcare providers of any recent opioid use. An opioid-free duration of a minimum of 7-10 days is recommended for patients to avoid precipitation of opioid withdrawal that may be severe enough to require hospitalization (see product information for Vivitrol® for more detail). Participants will be advised to be off all opioids, including opioid-containing medicines, for a minimum of 7 – 10 days before starting Vivitrol® in order to avoid precipitation of opioid withdrawal, opioid use will be based in self-report and urine drug screen during baseline and before treatment initiation, only those participants showing absence of opioid in urine will initiate treatment with Vivitrol®. For those patients transitioning from buprenorphine or methadone they may be vulnerable to precipitation of withdrawal symptoms for as long as two weeks. Healthcare providers will therefore inquiry about any recent use of opioids or any history of opioid dependence before starting Vivitrol® to avoid precipitation of opioid withdrawal.

Hepatotoxicity: Cases of hepatitis and clinically significant liver dysfunction were observed in association with Vivitrol® treatment during the clinical development program and in the postmarketing period. Discontinue use of Vivitrol® in the event of symptoms or signs of acute hepatitis (see product information for Vivitrol® for more detail). The results of liver function tests and CBC prior to the 2nd and 3rd Vivitrol injections will serve as safety monitoring for treatment-emergent AEs and to better inform the clinical judgment regarding the safety of continued dosing of Vivitrol in the present study.

Depression and Suicidality: Monitor patients for the development of depression or suicidal thinking (see product information for Vivitrol® for more detail).

When Reversal of Vivitrol® Blockade Is Required for Pain Management: In an emergency situation in patients receiving Vivitrol®, suggestions for pain management include regional analgesia or use of non-opioid analgesics (see product information for Vivitrol® for more detail).

Study staff will recommend participants to inform their primary care physician/clinic of their participation on this study. Alternatively, if participants are agreeable (i.e. during the informed consent), study staff will notify their primary care physician(s) or specialist(s) of their participation in this study. Additionally, a wallet card will be provided to participants in this study to alert medical personnel to the fact that they are taking Vivitrol[®].

Physicians should include the following issues in discussions with participants/patients for whom they prescribe Vivitrol®:

Advise patients that if they previously used opioids, they may be more sensitive to lower doses of opioids and at risk of accidental overdose should they use opioids when their next dose is due, if they miss a dose, or after Vivitrol® treatment is discontinued. It is important that patients inform family members and the people closest to the patient of this increased sensitivity to opioids and the risk of overdose.

Advise patients that because Vivitrol® can block the effects of opioids, patients will not perceive any effect if they attempt to self-administer heroin or any other opioid drug in small doses while on Vivitrol®. Further, emphasize that administration of large doses of heroin or any other opioid to try to bypass the blockade and get high while on Vivitrol® may lead to serious injury, coma, or death.

Patients on Vivitrol® may not experience the expected effects from opioid-containing analgesic, antidiarrheal, or antitussive medications.

Advise patients that a reaction at the site of Vivitrol® injection may occur. Reactions include pain, tenderness, induration, swelling, erythema, bruising, or pruritus. Serious injection site reactions including necrosis may occur. Some of these injection site reactions have required surgery. Patients will receive their injection from a healthcare provider qualified to administer the injection. Patients should be advised to seek medical attention for worsening skin reactions.

Advise patients that they should be off all opioids, including opioid-containing medicines, for a minimum of 7 – 10 days before starting Vivitrol® in order to avoid precipitation of opioid withdrawal. Patients transitioning from buprenorphine or methadone may be vulnerable to precipitation of withdrawal symptoms for as long as two weeks. Ensure that patients understand that withdrawal precipitated by administration of an opioid antagonist may be severe enough to require hospitalization if they have not been opioid-free for an adequate period of time, and is different from the experience of spontaneous withdrawal that occurs with discontinuation of opioid in a dependent individual. Advise patients that they should not take Vivitrol® if they have any symptoms of opioid withdrawal. Advise all patients, including those with alcohol dependence, that it is imperative to notify healthcare providers of any recent use of opioids or any history of opioid dependence before starting Vivitrol® to avoid precipitation of opioid withdrawal.

Advise patients that Vivitrol® may cause liver injury. Patients should immediately notify their physician if they develop symptoms and/or signs of liver disease.

Advise patients that they may experience depression while taking Vivitrol®. It is important that patients inform family members and the people closest to the patient that they are taking Vivitrol® and that they should call a doctor right away should they become depressed or experience symptoms of depression.

Advise patients to carry documentation to alert medical personnel to the fact that they are taking Vivitrol® (naltrexone for extended-release injectable suspension). This will help to ensure that patients obtain adequate medical treatment in an emergency.

Advise patients that Vivitrol® may cause an allergic pneumonia. Patients should immediately notify their physician if they develop signs and symptoms of pneumonia, including dyspnea, coughing, or wheezing.

Advise patients that they should not take Vivitrol® if they are allergic to Vivitrol® or any of the microsphere or diluent components.

Advise patients that they may experience nausea following the initial injection of Vivitrol®. These episodes of nausea tend to be mild and subside within a few days post-injection. Patients are less likely to experience nausea in subsequent injections. Patients should be advised that they may also experience tiredness, headache, vomiting, decreased appetite, painful joints and muscle cramps.

Advise patients that because Vivitrol® is an intramuscular injection and not an implanted device, once Vivitrol® is injected, it is not possible to remove it from the body.

Advise patients that Vivitrol[®] has been shown to treat alcohol and opioid dependence only when used as part of a treatment program that includes counseling and support.

Advise patients that dizziness may occur with Vivitrol® treatment, and they should avoid driving or operating heavy machinery until they have determined how Vivitrol® affects them.

Other events were observed during the Vivitrol® Clinical Studies (in alcohol- and/or opioid-dependent subjects treated with Vivitrol®), including events for which a drug cause was remote, events that were so general as to be uninformative, and those events reported only once that did not have a substantial probability of being acutely life-threatening (see product information for Vivitrol® for more detail).

Adverse Events Reporting

In the event of a serious adverse event (SAE), whether related to study drug or not, the Principal / Qualified investigator will notify REB of its occurrence and will submit the necessary documentation to their attention within timelines provided in CAMH SOP HSR207 Serious Adverse Event (SAE) Reporting. Only SAEs that are Serious unexpected adverse drug reaction (SUADR) will be reported to Health Canada as outlined in ICH E2A Clinical Safety Data Management Definitions and Standards for Expediting Reporting. While only SAEs and SUADRs will be reported as documented above, every adverse event will be assessed and recorded in the subject's research record by research staff working on the study and reviewed regularly by the Principal/Qualified Investigator. AEs will be documented and reported as mandated by current regulations.

The trial will be conducted in compliance with protocol, GCP, and applicable regulatory requirements.

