This project will test the safety and effectiveness of long term (i.e. 12 weeks) administration of the injectable extended-release of naltrexone; Vivitrol[®]. Vivitrol[®] is primarily used in the management of alcohol and opioid dependence. Naltrexone maintenance (e.g. oral) seems a promising treatment for cannabis use disorder (CUD). Therefore, administering Vivitrol[®] may have therapeutic properties for treatment of cannabis use disorder. The data collected will be used to ensure that the administration schedule we have planned for the subsequent future randomized clinical trials is appropriate.

In this study we will focus on the tolerability and effectiveness of the antagonist at the μ -opioid receptor, Vivitrol[®], to reduce cannabis use, increase abstinence rates and reduce cannabis withdrawal and craving.

OVERVIEW

[figure not shown]
The study will be open label, with no placebo control. Ten male and female subjects seeking treatment for cannabis dependence subjects will undergo study procedures as outlined below. Treatment with Vivitrol[®] will start at day 1 (week 1) and a target quit date will be set up at Day 7 (but subjects will be allowed to stop using cannabis before if they are willing and able to). There will be a total of 12 weeks (3 injections, 1 every 4 weeks) of exposure to Vivitrol[®]. Study visits will occur weekly during the medication phase of the study. Motivational Enhancement Therapy and Cognitive Behavioral Therapy (MET/CBT) will also start at Week 1 and therefore, all participants will receive a combination of pharmacotherapy (Vivitrol[®] 4 mL intramuscular injection) associated with MET/CBT for 12-weeks in accordance with the intervention practices shown to be effective in treatment of cannabis dependence [54]. The intervention will be adapted from the Brief Counseling for Marijuana Dependence manual published by the Substance Abuse and Mental Health Services Administration (SAMHSA). In addition, to ensure compliance a Contingency Management plan will be implemented with \$5 voucher that will be provided at each visit that is attended and at which biological samples have been provided, but with 5\$ voucher loss for a missed appointment. The vouchers will be provided at end of treatment phase and at end of the follow-up phase.

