At study visits, vital signs and self-report ratings will be collected. The subjects will have to come once per week (during treatment phase) to the center to assess cannabis and other substances usage

and will be asked to provide urine samples (see Summary of Study Assessments). As there may be compliance issues, a contingency management approach will be also implemented.

Following the medication phase, participants will have a follow-up weekly for another four weeks and then monthly until the 3 month follow up visit after the treatment starting date. We are planning to enroll 10 subjects.

Study Flow Schema

*Please see Summary of Study Assessments for tests administered during this period

Subjects will be pre-screened initially during a telephone interview in which basic medical, psychiatric, and substance abuse histories will be obtained without personal identifiers, contact information will be collected only for eligible participants as for pre-screening. The qualified subjects will then be assessed using the Structured Clinical Interview for *DSM 5* (SCID) and we will assess presence of CUD using *DSM 5* criteria. We will enroll a total of 10 subjects, that will be treated open-label (non blinded) with Vivitrol 380 mg.

Experimental group	Experimental condition	
Group #1 (n=10)	Vivitrol® 380 mg, 4 mL intramuscular injection + MET/CBT	

Summary of Study Assessments

Assessment	Baseline	Weekly (Weeks 1-12)	Weekly (Weeks 13-16)	Monthly (months 5-6)
Informed Consent	X			
Psychiatric Evaluation (including				
SCID)	Х			
DSM5 criteria for CUD	Х	X (week 12 only)	X (week 13 only)	X (end of trial)
Demographic	Х	· · · ·		
Bloodwork (including CBC),		X (prior to 2 nd and 3 rd		X (end of trial)
Urinalysis	Х	Vivitrol injections)		
EKG	Х	X (week 1 only)		X (end of trial)
Physical Exam	Х			X (end of trial)
Urine Toxicology	X	X (before Vivitrol administration)	Х	Х
Vital Signs, Carbon Monoxide	Х	Х	Х	Х
Serum Pregnancy Test (Females only)	Х	If needed	If needed	If needed
Urine Pregnancy Test (Females only)	Х	Х	Х	Х
FTND, Cigarette, alcohol and caffeine Time-line Follow-Back (TLFB)	Х	Х	X	X
Smoking Diary	Х	Х	Х	Х
Cannabis TLFB, Marijuana withdrawal checklist (MWC), Marijuana Craving Questionnaire (MCQ)	Х	Х	Х	X

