- Pregnant or breast-feeding
- Positive urine drug test for opioids (including methadone, morphine, buprenorphine) or benzodiazepines (unless prescribed) at baseline
- Any IM gluteal administration 30 days prior to baseline
- Participation in a clinical trial of a pharmacological agent within 30 days prior to baseline
- Known intolerance and/or hypersensitivity to naltrexone, carboxymethylcellulose, or polylactide-coglycolide
- Any finding that, in the view of the principal investigator, would compromise the subject's ability to fulfill the protocol visit schedule or visit requirement (e.g. unadjudicated charges and/or pending parole hearings)

Pre-study Screening and Baseline/follow up evaluations and questionnaires that will be used:

- a) Structured Clinical Interview for DSM 5 severe mental disorders, including substance-related and addictive disorders, other than CUD, tobacco use disorder, and caffeine-related disorders.
- b) DSM 5 Criteria for CUD for the past month at baseline, end of treatment and end of follow-up
- c) Demographic assessments.
- d) Psychiatric/Medical Evaluation and Physical Examination by study physician Weight (kg) and Vital Signs (Temperature, Pulse, Blood Pressure and Respiration Rate). Carbon monoxide will be taken at each study visit to assess exposure to smoke (will reflect both cannabis and tobacco exposure).
- e) 12-lead Electrocardiogram (EKG).
- f) Blood work, including complete blood count (CBC), electrolytes, renal and liver function tests will be carried out at baseline and prior to the 2nd and 3rd Vivitrol injections.
- g) For female subjects, a serum pregnancy test (beta-HCG) at inclusion (and when deemed needed) and weekly urine pregnancy test will be performed. Female subjects will be asked if they are lactating.
- h) Ten-panel urine toxicology screen at baseline, and at each study visit to ensure absence of illicit drug use.
- i) Substance use assessment including the age of first use, age of regular use, number of days in the past 30 days that the substance was used, number of days in the past week that the substance use used, and the amount of the substance used per using day (i.e. joints per day for cannabis).

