Pharmacological Treatment: Vivitrol[®] 380 mg, 4 mL intramuscular injection Pilot Study in 10 subjects:

There is currently limited information to guide us on the Vivitrol[®] dosage to use in cannabis dependent individuals that likely have developed strong tolerance to cannabinoids. We are planning to administer Vivitrol[®] (380 mg, 4 mL intramuscular injection) every 4 weeks. Only eligible participants will be administered study medication (i.e. as per inclusion/exclusion criteria). On the day of the scheduled injection of Vivitrol[®] participants will be observed by qualified staff (i.e. staff performing injection) for 5-10 minutes for possible injection site reactions. Following injection of study medication the subjects will remain at CAMH facility for rest of study assessments (approx. 30 min to 1 h), so study staff will be able to monitor possible systemic AEs post-dosing. Medications and supportive measures will be available at CAMH clinic as per expected side effects of study medication. Additionally, participants in the study will be regularly assessed during the trial (see above schedule of assessments) for changes in health status, these assessments include ECG, vitals and CBC. The subjects in this study will be treatment-seekers that fit our inclusion/exclusion criteria and that will be treated open-label to ensure good tolerability. These 10 subjects will allow us to determine if our schedule for dosing is appropriate for the subsequent RCTs.

Biological sample collection (excludes samples used for general health assessments)

Urine samples will be collected weekly. All participants will have urine samples collected on the weekly visit. At any point that biological samples are taken, information about the last time the participant may have smoked cannabis and last used the study medication will be collected. All urine samples will be taken at the beginning of the visit to standardize the time. Each urine sample obtained will have creatinine measures and THC quantification determined by the CAMH laboratory. Appropriate temperature control until analysis will be maintained.

Biological sample collection for general health assessments

Urine and blood samples for general health assessments will be collected at Baseline and at the end of trial (see Summary of Study Assessments).

Psychological support: MET/CBT intervention

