All personal study participant data collected and processed for the purposes of this study will be managed by the investigators and their research staff with adequate precautions to ensure the confidentiality of this data, and in accordance with applicable national and local laws and regulations on personal data protection. Study data will be de-identified or coded. A master linking log with identifiers will be kept and stored separately from the data. The ethics committees approving this research and Health Canada will be granted direct access to the study participant's original medical records for verification of clinical trial procedures and/or data, without violating the confidentiality of the subjects, to the extent permitted by the law and regulations. In any presentations of the results of this study at meetings or in publications, the subject's identity will remain confidential.

Summary of risks and benefits to subjects:

Risks Associated with the Medication

Vivitrol® is a medication approved by the U.S. Food and Drug Administration for the treatment of alcohol and opioid dependence. Therefore, current evidence shows only the risks of using Vivitrol® associated with opioid and alcohol dependence. The risks of using Vivitrol® associated with cannabis use disorder are still unknown. Research staff and study physicians will be made aware of the serious adverse reactions that may be associated with Vivitrol® therapy in clinical use, which include: severe injection site reactions, eosinophilic pneumonia, serious allergic reactions, unintended precipitation of opioid withdrawal, accidental opioid overdose and depression and suicidality.

The adverse events seen most frequently in association with Vivitrol® therapy for alcohol dependence (i.e., those occurring in \geq 5% and at least twice as frequently with Vivitrol® than placebo) include nausea, vomiting, injection site reactions (including localized swelling, itching of the skin, nodules and swelling), muscle cramps, dizziness or syncope, somnolence or sedation, anorexia, decreased appetite or other appetite disorders.

The adverse events seen most frequently in association with Vivitrol® therapy in opioid-dependent patients (ie, those occurring in $\geq 2\%$ and at least twice as frequently with Vivitrol® than placebo) were hepatic enzyme abnormalities, injection site pain, nasopharyngitis, insomnia, and toothache.

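### No liver test is scheduled between the third injection and end of trial, a gap of about 16 to 18 weeks if end of trial is the month 6 visit

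*Combined protocol and SAP*

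**What the plan says.** The Overview sets the dosing: "There will be a total of 12 weeks (3 injections, 1 every 4 weeks) of exposure to" the study drug, starting on day 1.

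Liver tests and bloodwork appear in four places:

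- **Pre-study Screening and Baseline/follow up evaluations, item f:** "renal and liver function tests will be carried out at baseline and prior to the 2nd and 3rd Vivitrol injections".
- **Summary of Study Assessments:** the row that begins "Bloodwork (including CBC" is marked at baseline, in weeks 1-12 only before injections 2 and 3, not at all in weeks 13-16, and then at end of trial. That last mark is in the column headed "Monthly (months 5-6".
- **The second Biological sample collection section, on general health samples:** its one sentence reads "Urine and blood samples for general health assessments will be collected at Baseline and at the end of trial (see Summary of Study Assessments".
- **Hepatotoxicity paragraph of the risk section:** the tests before injections 2 and 3 "will serve as safety monitoring for treatment-emergent AEs and to better inform the clinical judgment regarding the safety of continued dosing of Vivitrol".

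The Overview also describes follow-up as "weekly for another four weeks and then monthly until the 3 month follow up visit after the treatment starting date". This bears on when the trial ends.

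On frequency, Risks Associated with the Medication says that the most frequent events in opioid-dependent patients "were hepatic enzyme abnormalities, injection site pain, nasopharyngitis, insomnia, and toothache".

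**The concern.** The Hepatotoxicity paragraph gives the liver tests two jobs: detecting treatment-emergent events and informing the decision to give another dose. The second job ends at injection 3. The first does not, because the third dose brings its own exposure. Yet each scheduled on-treatment test looks back on one or two doses, and none looks back on three.

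The project sets out to test the safety of 12 weeks of administration and to judge whether the dosing schedule suits later randomised trials. It also says that the risks in cannabis use disorder are unknown. Followed exactly, the plan yields no liver result near the end of the regimen it is meant to describe. A rise after dose 3 that causes no symptoms and resolves would leave no trace. A rise that persists would be found at end of trial, but its onset could be placed only somewhere between the draw before injection 3 and that visit. A subject lost to follow-up after week 13 would have no liver test after dose 3 at all.

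**Working it through.** The plan states no figure for this interval, so there is none to reproduce. The check is calendar arithmetic.

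**Inputs**

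- Three injections, one every 4 weeks from day 1 (Overview).
- Draws at baseline, before injection 2, before injection 3 and at end of trial (item f; Summary of Study Assessments; Biological sample collection for general health assessments).
- Assumption: a draw before an injection is taken either on the injection day or at the weekly visit before it.
- Assumption: the end-of-trial bloodwork includes liver function tests. Item f and the Hepatotoxicity paragraph name liver tests only for the earlier draws.

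**Injection days:** day = 1 + 28 × (k − 1), which gives days 1, 29 and 57.

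**Doses 1 and 2 to the next draw**

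- Dose 1: 29 − 1 = 28 days, or 22 − 1 = 21 days.
- Dose 2: 57 − 29 = 28 days, or 50 − 29 = 21 days.
- Each is therefore 3 to 4 weeks.

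**Dose 3 to the next draw:** gap in weeks = (end-of-trial day − 57) / 7, where the end-of-trial day is 1 + 7 × weeks since treatment start.

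| Reading of end of trial | Weeks since start | Day | Gap after dose 3 |
|---|---|---|---|
| Month 6, six 4-week months | 24 | 169 | 112 / 7 = 16.0 weeks |
| Month 6, six calendar months | 26 | 183 | 126 / 7 = 18.0 weeks |
| Month 5 | 20 | 141 | 84 / 7 = 12.0 weeks |
| 3 months after the 12-week medication phase | 24 to 25 | 169 to 176 | 16.0 to 17.0 weeks |
| 3 months after treatment start, read literally | 13 | 92 | 35 / 7 = 5.0 weeks |

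If the draw before injection 3 is taken on day 50, the interval between consecutive draws is one week longer in each row. Counting the end of week 24 as day 168 instead of day 169 shortens a gap by one day and changes nothing of substance.

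**Which reading fits?** The literal one conflicts with its own sentence. Four weekly visits after a 12-week medication phase run to week 16, which ends on day 16 × 7 = 112. That is 112 − 92 = 20 days after the supposed last visit. It also conflicts with the table's columns for weeks 13-16 and months 5-6. Three months after the end of medication falls at month 6, which agrees with the table.

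**Timing of a week 13 draw:** days 85 to 91, so 85 − 57 = 28 to 91 − 57 = 34 days after dose 3. This is close to the interval already used after doses 1 and 2.

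**The case against.** The main counter-argument is that little hangs on the missing test. There is no fourth injection, so a week 13 result could change no dose. The primary tolerability outcome counts dropouts due to serious adverse events and does not use laboratory values. Every repeat dose already has a liver test before it, and the protocol promises no end-of-treatment test. In a 10-subject, open-label, single-arm pilot, what is lost is descriptive safety detail. All of this is correct, and it limits the weight of the point.

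The risk evidence can also be questioned. Hepatic enzyme abnormalities are on the list for opioid-dependent patients but not on the parallel list for alcohol-dependent patients. This trial excludes subjects with an opioid-positive baseline urine test and requires subjects to be otherwise healthy on labs. The opioid list is therefore weak support on its own. The general hepatotoxicity warning still applies, and the protocol itself adopted liver monitoring because of it.

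Other follow-up continues: SAFTEE weekly through week 13 and at end of trial, vital signs at every visit, recording and review of all adverse events, a physical exam at end of trial, and advice to report symptoms of liver disease. None of these detects an enzyme rise without symptoms.

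Finally, the size depends on an unclear end date, and under the literal 3-month reading the gap nearly disappears. That reading does not survive comparison with the visit schedule. The other uncertainty, whether end-of-trial bloodwork includes liver tests, could only lengthen the gap.

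**Conclusion.** The concern holds. No liver test is scheduled between injection 3 and end of trial. The gap is 16 to 18 weeks if end of trial is the month 6 visit, which is the reading best supported by the table, and 12 weeks if it is month 5. The comparable interval after doses 1 and 2 is 3 to 4 weeks. The conclusion assumes that injections are given on schedule and that the end-of-trial bloodwork includes liver tests.

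The consequence is an incomplete safety description of the three-dose regimen and weaker follow-up of any affected subject. Dosing, the primary outcomes and the efficacy analyses are untouched. The documents give no rate of symptomless enzyme rises after a third dose, so no expected number of missed cases can be stated. This is an improvement the sponsor should make, because the risk is one the protocol names and the remedy is cheap.

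**What to change.** Add bloodwork with liver function tests at the week 13 visit. That visit already includes SAFTEE, the DSM-5 criteria, the ASI and the WHODAS, so no new visit is needed. The cost is one extra draw per subject, 10 in all.

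State end of trial as a week number, and reword the Overview's follow-up sentence to agree with the Summary of Study Assessments. Say explicitly that the end-of-trial bloodwork includes liver function tests.

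As optional tidying, list the same draws in item f, in the table row and in the section on samples for general health assessments. These last changes are wording only.
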